5.2 SAMPLE STORAGE, TRACKING AND DISPOSITION

Samples will be ordered in CRIS and tracked through a Clinical Trial Data Management system. Should a CRIS screen not be available, the CRIS downtime procedures will be followed. Samples will not be sent outside NIH without IRB notification and an executed MTA.

- Specimens will be collected and analyzed as noted above.
- Samples will be labeled with the date and time of acquisition, the type of tissue and patient study number in the Labmatrix database.
- Tissue will be stored in the NCI Endocrine Oncology lab.
- At the completion of the protocol, the investigator will dispose of all specimens in accordance with the environmental protection laws, regulations and guidelines of the Federal Government and the State of Maryland. Any loss or unintentional destruction of the samples will be reported to the IRB.
- No samples will be stored for ongoing and future research on this protocol.
- Patients who are willing to have samples stored for future and ongoing research will be enrolled on 09-C-0242 *Prospective Comprehensive Molecular Analysis of Endocrine Neoplasms*.

6 DATA COLLECTION AND EVALUATION

6.1 DATA COLLECTION

Data prior to and during the course of the patient's participation will be collected in order to monitor patient eligibility, and will include review of medical and family history records, non-invasive imaging, blood work, and urinary studies. Data will be securely stored in the Labmatrix database.

All details of patient evaluation, management and treatment will be documented in the patient medical record. Only the following information will be captured on the CRFs:

- Detailed demographic information including family history
- Laboratory results
- Imaging results (CT scan)

The PI will be responsible for overseeing entry of data into an in-house password protected electronic system and ensuring data accuracy, consistency and timeliness. The principal investigator, associate investigators/research nurses and/or a contracted data manager will assist with the data management efforts. All data obtained during the conduct of the protocol will be kept in secure network drives or in approved alternative sites that comply with NIH security standards. Primary and final analyzed data will have identifiers so that research data can be attributed to an individual human subject participant.

End of study procedures: Data will be stored according to HHS, FDA regulations, and NIH Intramural Records Retention Schedule as applicable.

Loss or destruction of data: Should we become aware that a major breach in our plan to protect subject confidentiality and trial data has occurred, the IRB will be notified.

6.2 DATA SHARING PLANS

6.2.1 Human Data Sharing Plan

I will share de-identified human data generated in this research for future research

- in a NIH-funded or approved public repository clinicaltrials.gov
- in BTRIS
- in publication and/or public presentations
- at the time of publication or shortly thereafter.

6.3 TOXICITY CRITERIA

The following adverse event management guidelines are intended to ensure the safety of each patient while on the study. The descriptions and grading scales found in the revised NCI Common Terminology Criteria for Adverse Events (CTCAE) version 4.0 will be utilized for AE reporting. All appropriate treatment areas should have access to a copy of the CTCAE version 4.0. A copy of the CTCAE version 4.0 can be downloaded from the CTEP web site

(http://ctep.cancer.gov/protocolDevelopment/electronic_applications/ctc.htm#ctc_40).

7 SAFETY REPORTING REQUIREMENTS/DATA AND SAFETY MONITORING PLAN

All patients will undergo monitoring of their disease, operative intervention when indicated, and follow up as per standard of care. Patients who meet the standard of care criteria for resection of their disease will undergo a major operative procedure and may receive extensive care in the ICU. The principal investigator or designee will closely monitor and document the clinical care and treatment of each patient as per standard of care at the NIH Clinical Center. As per NIH Clinical Center standards of practice, the Occurrence Reporting System will be used to report any clinical events meeting these reporting criteria.

Patients who meet specific criteria described in Section 3.2 will undergo an adrenal biopsy. Adverse events will be collected in this cohort only from the time of the biopsy through 30 days post biopsy or until the date of surgery, whichever comes first. (No adverse events will be collected or reported on this protocol for patients undergoing standard of care procedures.)

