There are no reliable preoperative clinical, imaging or biochemical tests available to distinguish between primary benign and malignant adrenocortical neoplasms in the absence of obvious metastatic disease or locoregional invasion [5]. Imaging features such as tumor heterogeneity, irregular tumor border, hemorrhage, necrosis, rapid tumor growth rate, tumor Hounsfield unit $>10-20$ on non-contrast CT scan, and intravenous contrast washout of 40% or less after 15 minutes are more common in malignant tumors but are not reliable enough to avoid the need for adrenalectomy to exclude a cancer diagnosis nor to forgo continued follow up [5-10]. In patients with a history of an extra-adrenal malignancy, an adrenal incidentaloma may indicate metastatic disease in 32% to 73% of cases depending on the primary tumor site and patient age [1, 11]. The tumor size of adrenal neoplasm measured by imaging studies has been used as a preoperative surrogate marker for a malignant tumor and for recommending resection, but this criterion is not precise for tumors that measure > 2 cm but < 6 cm [2, 12]. Even when the tumor is 6 cm or larger, the reported risk of malignancy ranges from 5% to 98%, depending on the study cohort [5, 13, 14]. In many centers, a size threshold of > 6 cm has been used as an absolute indication for adrenalectomy. However, it is unclear whether adrenal tumors between 2 cm and 6 cm should be removed or monitored, whereas most experts recommend monitoring tumors < 4 cm in size depending on the patient’s age.

Fine needle aspiration biopsy and cytologic examination has not been routinely used to evaluate adrenal neoplasm at most centers because it is not accurate enough for

distinguishing between primary benign and malignant adrenocortical tumors [15-19]. However, in patients with a concurrent malignancy or history of extra-adrenal malignancy, fine needle aspiration biopsy may be useful for detecting metastatic disease to the adrenal gland after biochemical exclusion of a hyperfunctioning tumor, especially a pheochromocytoma [15-19]. Fine needle aspiration of the adrenal gland is associated with a low risk (<1%) of complications such as bleeding, pneumothorax, pain, and rarely tumor seeding along the needle track [1, 20].

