3.2 CT GUIDED FINE NEEDLE ASPIRATION BIOPSY OF ADRENAL NEOPLASM

- Patients with confirmed non-functional tumors greater than 2 cm in greatest dimension will undergo CT guided fine needle aspiration in the Interventional Radiology Department as per standard of care if they do not require an adrenalectomy.
- Tissue will be handled as described in Section [5.1.1](#)

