3.4 FOLLOW-UP EXAMINATIONS

3.4.1 Patients who are found to have an adrenal neoplasm which does not require resection will undergo the following evaluations every year for 5 years:

- Physical exam to include vital signs and ECOG status
- Laboratory evaluations - all tumors
 - 24-hour urinary cortisol level
 - Low dose (1-2mg) dexamethasone suppression test
 - Serum fractionated plasma normetanephrine and metanephrine
 - Serum renin and plasma aldosterone levels
- Adrenal protocol CT scan with and without intravenous contrast.

3.4.2 Patients who undergo an adrenalectomy will undergo the following evaluations every year for 5 years (only if found to be malignant on histopathology):

- Physical exam to include vital signs and ECOG status
- Laboratory Evaluations
 - 24-hour urinary cortisol level
 - Low dose (1mg) dexamethasone suppression test (only for those patients with non-functioning tumors)
- CT scan of the chest, abdomen and pelvis to exclude disease recurrence

Note: Patients who are unwilling or unable to travel to the NIH Clinical Center for follow up may have the examinations performed at home with the results sent to the research team.

Note: Patients may be evaluated on a more frequent basis if they develop symptoms possibly associated with their adrenal neoplasm. Patients who meet the criteria for adrenalectomy at any time during the follow up period will be offered surgical intervention at the NIH Clinical Center. Patients who require chemotherapy will be offered a clinical trial at the NIH Clinical Center if they are eligible, or will be referred to their home oncologist for care.

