7.1 DEFINITIONS

7.1.1 Adverse Event

An adverse event is defined as any reaction, side effect, or untoward event that occurs during the course of the clinical trial associated with the use of a drug in humans, whether

or not the event is considered related to the treatment or clinically significant. For this study, AEs will include events reported by the patient, as well as clinically significant abnormal findings on physical examination or laboratory evaluation. A new illness, symptom, sign or clinically significant laboratory abnormality or worsening of a pre-existing condition or abnormality is considered an AE.

All AEs, including clinically significant abnormal findings on laboratory evaluations, regardless of severity, will be followed until return to baseline or stabilization of event. Serious adverse events that occur more than 30 days after the intervention and have an attribution of at least possibly related to the intervention should be recorded and reported.

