9.4 EVALUATION OF BENEFITS AND RISKS/DISCOMFORTS

Participants may experience no personal benefit from the study. There is however the potential benefits of increasing our ability to diagnose and predict the outcome of patients with malignant adrenocortical neoplasms. Each individual patient would have a complication risk of <1% associated with the fine needle aspiration biopsy.

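### Biopsy adverse events are to be collected to day 30, but no contact is scheduled in that window and the CRF list has no place for them, so complications managed elsewhere may be missed.

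*Combined protocol and SAP*

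**What the plan says.** **Who is biopsied.** Section 3.2: "Patients with confirmed non-functional tumors greater than 2 cm in greatest dimension will undergo CT guided fine needle aspiration", provided they do not need an adrenalectomy. The section then refers to tissue handling and ends.

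**What is promised.** Section 7: "Adverse events will be collected in this cohort only from the time of the biopsy through 30 days post biopsy". Surgery before day 30 closes the window early. Section 7.1.1 gives the sources: "AEs will include events reported by the patient, as well as clinically significant abnormal findings on physical examination or laboratory evaluation".

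**What is scheduled next.** Section 3.4.1, on unresected patients, reads: "Patients who are found to have an adrenal neoplasm which does not require resection will undergo the following evaluations every year for 5 years". A note in Section 3.4 allows more frequent evaluation for symptoms that may come from the neoplasm. Another lets patients who cannot or will not travel have follow-up examinations at home.

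**What is recorded.** Section 6.1 restricts the CRFs to demographics with family history, laboratory results and CT imaging.

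**What is reported.** All four adverse event lines of the continuing-review table in Section 7.2.2 use the window from biopsy to day 30 or surgery.

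**The stated risk.** Section 9.4: "Each individual patient would have a complication risk of <1% associated with the fine needle aspiration biopsy". Section 1.2 gives the same figure with literature citations: "Fine needle aspiration of the adrenal gland is associated with a low risk (<1%) of complications".

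**The concern.** The protocol sets a collection window and names the sources of information, but schedules nothing inside the window that would produce that information. No examination or laboratory test is planned in those 30 days, so two of the three sources in Section 7.1.1 have no planned occasion. The third, the patient's report, depends on the patient calling in. At the first yearly evaluation, a patient would have to recall and date an event from about 11 months earlier.

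What is at stake is the count of harms from a procedure that Section 9.4.2 describes as done only for research. The IRB sees that count at continuing review. A low count obtained this way could be read as support for the <1% figure when it partly reflects silence.

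**Working it through.** **Step 1: schedule against window.**

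| Time | Planned contact or test, biopsied and unresected patient | Source |
|---|---|---|
| Biopsy day | Biopsy at the NIH Clinical Center | 3.2, 5.1.1 |
| After biopsy day, to day 30 | None stated | 3.2, 3.4.1 |
| Yearly for 5 years | Examination, hormone tests, adrenal CT | 3.4.1 |

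A patient who goes to surgery within 30 days has a contact then, so the gap concerns biopsied patients who stay under observation.

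**Step 2: the plan's own figure.** The <1% risk is cited, with no numerator or denominator, so it cannot be reproduced. Section 8 contains no complication analysis. The number of biopsies is not stated; planned accrual of 500 is an upper bound.

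**Step 3: illustration of under-ascertainment.** The inputs below are assumptions, since the documents give none of them.
- Biopsies: n = 200.
- True complication rate: p = 0.02, twice the stated ceiling.
- Share of events missed: m.

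Reported events follow X ~ Binomial(n, p(1 − m)). Because the protocol says <1%, the criterion is a rate strictly below 1%, which at n = 200 means X ≤ 1:

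P(X ≤ 1) = (1 − q)^200 + 200·q·(1 − q)^199, with q = 0.02(1 − m).

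- m = 0, q = 0.020: 0.0176 + 0.0718 = 0.089, or 9%.
- m = 0.10, q = 0.018: 0.0264 + 0.0969 = 0.123, or 12%.
- m = 0.50, q = 0.010: 0.1340 + 0.2707 = 0.405, or 40%.

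The range over n and m, by the same exact binomial calculation with a true rate of 2%:

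| n | none missed | 10% missed | 25% missed | 50% missed | 75% missed |
|---|---|---|---|---|---|
| 100 | 13% | 16% | 22% | 37% | 61% |
| 200 | 9% | 12% | 20% | 40% | 74% |
| 300 | 6% | 9% | 17% | 42% | 81% |
| 400 | 4% | 7% | 15% | 43% | 86% |

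With none missed, more biopsies expose a wrong figure (13% falls to 4%). With half missed, more biopsies do not help (37% rises to 43%), because the reported rate settles at 0.02 × 0.5 = 1%.

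**Step 4: precision even with complete reporting.** With zero events, the one-sided 95% upper bound is 1 − 0.05^(1/n). It falls below 1% at n = 299 (0.997%). At n = 200 it is 1.49%, and the two-sided exact upper limit is 1 − 0.025^(1/200) = 1.83%. At a true rate of 1%, only 200 × 0.01 = 2 events are expected in 200 biopsies, so one or two missed events decide what the table appears to show.

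**The case against.** **Existing safeguards.** Section 7 says the investigator or a designee will closely monitor each patient's care and that the Occurrence Reporting System is used. Section 7.1.1 requires events to be followed to resolution or stabilization, and possibly related serious events after day 30 to be recorded and reported. Section 7.2.1 requires reports of deaths other than from progressive disease, and Section 7.3.1 has the team meet to discuss each patient. These provisions stand, and they narrow the gap mainly to events treated elsewhere and not volunteered. They do not close it: none sets a date or a contact, and each can act only on what the study has already been told.

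**Operational detail.** A post-biopsy call could sit in site procedures, and Section 3.2 describes the biopsy as standard of care. That is possible. However, Section 9.4.2 calls the biopsy research-only, and the commitment to collect events is in the protocol, so the means of meeting it belongs there too.

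**Stronger readings.** A reader might infer that the <1% risk cannot be checked at all. The documents do not support that: biopsy-day and volunteered events would still come to notice, and estimating the rate is not an objective in Section 1.1 or an analysis in Section 8. Nor does feasibility in Section 1.1.1 extend to safety; it concerns molecular testing of the samples. The home-examination note in Section 3.4 says nothing about treating biopsy complications elsewhere, so that remains an inference. Finally, counting a rate of exactly 1% as confirming <1% would raise the figures at n = 200 to 24% (none missed) and 68% (half missed), but the protocol's wording is strict.

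**Unseen material.** Appendix C and some figures are missing from the text reviewed. Their titles (work-up and adrenalectomy algorithm; specimen flow) make a post-biopsy contact there unlikely.

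**Conclusion.** The gap is real: a 30-day collection window with no scheduled contact inside it for patients under observation, and no adverse event item in the CRF list. The consequence is possible under-counting in the Section 7.2.2 table and study data that could not reliably support the <1% figure. It is not an error in a primary or secondary analysis.

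The size is illustrative. It rests on an assumed 200 biopsies, an assumed true rate of 2% and an assumed share of events missed. If few are missed the effect is small (9% to 12%); the 40% figure depends on half being missed. The absence of a scheduled contact is certain in the text available; how many events it would lose is unknown. This is a cheap improvement.

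**What to change.** - **Sections 3.2 and 3.4:** schedule one telephone contact with every biopsied patient at about day 30, or immediately before surgery if earlier. Use a short standard list of questions: pain, bleeding, infection, breathing problems, and any unplanned care or admission.
- **Section 6.1:** add adverse events to the CRF list.
- **Section 7.2.2 and the final report:** tabulate complications over all biopsied patients with an exact 95% interval, and report the proportion successfully contacted separately. A denominator of contacted patients only could drop those unreachable because they are in hospital or have died.

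The cost is one short call per biopsied patient by existing research staff and one CRF item. The recorded event rate may rise slightly. Eligibility, treatment and the primary analysis do not change.

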7.1 DEFINITIONS

7.1.1 Adverse Event

An adverse event is defined as any reaction, side effect, or untoward event that occurs during the course of the clinical trial associated with the use of a drug in humans, whether

or not the event is considered related to the treatment or clinically significant. For this study, AEs will include events reported by the patient, as well as clinically significant abnormal findings on physical examination or laboratory evaluation. A new illness, symptom, sign or clinically significant laboratory abnormality or worsening of a pre-existing condition or abnormality is considered an AE.

All AEs, including clinically significant abnormal findings on laboratory evaluations, regardless of severity, will be followed until return to baseline or stabilization of event. Serious adverse events that occur more than 30 days after the intervention and have an attribution of at least possibly related to the intervention should be recorded and reported.

7.1.2 Suspected adverse reaction

Suspected adverse reaction means any adverse event for which there is a reasonable possibility that the research procedure caused the adverse event. For the purposes of safety reporting, ‘reasonable possibility’ means there is evidence to suggest a causal relationship between the research procedure and the adverse event. A suspected adverse reaction implies a lesser degree of certainty about causality than adverse reaction, which means any adverse event caused by a research procedure.

7.1.3 Unexpected adverse reaction

An adverse event or suspected adverse reaction is considered “unexpected” if it is not consistent with the risk information described in the general investigational plan or elsewhere in the current application.

7.1.4 Serious

An Unanticipated Problem or Protocol Deviation is serious if it meets the definition of a Serious Adverse Event or if it compromises the safety, welfare or rights of subjects or others.

7.1.5 Serious Adverse Event

An adverse event or suspected adverse reaction is considered serious if in the view of the investigator it results in any of the following:

- Death,
- A life-threatening adverse drug experience
- Inpatient hospitalization or prolongation of existing hospitalization
- Persistent or significant incapacity or substantial disruption of the ability to conduct normal life functions
- A congenital anomaly/birth defect.
- Important medical events that may not result in death, be life-threatening, or require hospitalization may be considered a serious adverse drug experience when, based upon appropriate medical judgment, they may jeopardize the patient or subject and may require medical or surgical intervention to prevent one of the outcomes listed in this definition.

7.1.6 Disability

A substantial disruption of a person's ability to conduct normal life functions.

7.1.7 Protocol Deviation (NIH Definition)

Any change, divergence, or departure from the IRB-approved research protocol.

7.1.8 Non-compliance (NIH Definition)

The failure to comply with applicable NIH Human Research Protections Program (HRPP) policies, IRB requirements, or regulatory requirements for the protection of human research subjects.

7.1.9 Unanticipated Problem

Any incident, experience, or outcome that:

- Is unexpected in terms of nature, severity, or frequency in relation to
- (a) the research risks that are described in the IRB-approved research protocol and informed consent document; Investigator's Brochure or other study documents, and
- (b) the characteristics of the subject population being studied; AND
- Is related or possibly related to participation in the research; AND
- Suggests that the research places subjects or others at a greater risk of harm (including physical, psychological, economic, or social harm) than was previously known or recognized.

7.2 NCI-IRB AND CLINICAL DIRECTOR REPORTING

7.2.1 NCI-IRB and NCI CD Expedited Reporting of Unanticipated Problems and Deaths

The Protocol PI will report in the NIH Problem Form to the NCI-IRB and NCI Clinical Director:

- All deaths, except deaths due to progressive disease
- All Protocol Deviations
- All Unanticipated Problems
- All non-compliance

Reports must be received within 7 days of PI awareness via iRIS.

7.2.2 NCI-IRB Requirements for PI Reporting at Continuing Review

The protocol PI will report to the NCI-IRB:

1. A summary of all protocol deviations in a tabular format to include the date the deviation occurred, a brief description of the deviation and any corrective action.
2. A summary of any instances of non-compliance
3. A tabular summary of the following adverse events:

- All Grade 2 unexpected events that are possibly, probably or definitely related to the research that occur within 30 days of biopsy (or until day of surgery, whichever comes first)
- All Grade 3 and 4 events that are possibly, probably or definitely related to the research that occur within 30 days of biopsy (or until day of surgery, whichever comes first)
- All Grade 5 events regardless of attribution that occur within 30 days of biopsy (or until day of surgery, whichever comes first)
- All Serious Events regardless of attribution and occur within 30 days of biopsy (or until day of surgery, whichever comes first)

NOTE: Grade 1 events are not required to be reported.

